9 STATISTICAL ANALYSIS

9.1 General Considerations

The precision standards for reporting safety and efficacy variables are provided in an internal Biometrics document that specifies the programming rules including the precision for derived variables.

Data will be summarized by treatment group in the parent study (“Control in 445-104” and “ELX/TEZ/IVA in 445-104”) and overall (“Any ELX/TEZ/IVA”).

Continuous variables will be summarized using the following descriptive summary statistics: the number of subjects (n), mean, standard deviation (SD), median, minimum value (min), and maximum value (max).

Categorical variables will be summarized using counts and percentages. Percentages will be presented to 1 decimal place.

Baseline value for clinical laboratory values, standard 12-lead ECGs, vital signs, and pulse oximetry will be the TC safety baseline defined as the most recent non-missing measurement (scheduled or unscheduled) collected before the first dose of study drug in the parent study (if the subject actually received at least one dose of ELX/TEZ/IVA during the parent study) or the first dose of study drug in the OLS (if the subject did not actually receive at least one dose of ELX/TEZ/IVA during the parent study). **Baseline value** for efficacy analyses, demographics, and baseline characteristics will be the parent study baseline defined as the most recent non missing measurement (scheduled or unscheduled) collected before the first dose of study drug in the Treatment Period of the parent study.

Change (absolute change) from baseline will be calculated as post-baseline value – baseline value. **Relative change** from baseline will be calculated as (post-baseline value – baseline value)/baseline value.

Unscheduled visits: Unscheduled visit measurements will be included in analysis as follows:

- 1) In scheduled visit windows per specified visit windowing rules
- 2) In the derivation of baseline
- 3) In the derivation of maximum and minimum values during TE period for Part A, and maximum and minimum change from baseline values during TE period for Part A for the long-term safety analyses
- 4) In individual subject data listings as appropriate

Visit windowing rules: The analysis visit windows for protocol-defined visits are provided in Section 12.1.

Incomplete/missing data will not be imputed, unless specified otherwise.

Outliers: No formal statistical analyses will be performed to detect or remedy the presence of statistical outliers, unless specified otherwise.

Multiplicity: There will be no multiplicity adjustment as no hypothesis test is planned for safety analysis, unless specified otherwise.

9.2 Background Characteristics

9.2.1 Subject Disposition

A summary table of subject disposition in the OLS will be presented for the OL All Subjects Set for Part A by treatment group in parent study and overall with the following categories:

- Enrolled (OL All Subjects Set for Part A)
- Dosed (OL-SS for Part A)
- Enrolled and dosed (OL-FAS for Part A)

The number and percentage (based on OL-FAS for Part A) of subjects in each of the following disposition categories will be summarized by treatment group in parent study and overall:

- Completed Treatment
- Prematurely discontinued treatment and the reasons for discontinuation

- Completed study
- Prematurely discontinued the study and the reasons for discontinuation
- Rollover to Part B

A listing will be provided for subjects who discontinued treatment or who discontinued study with reasons for discontinuation.

9.2.2 Demographics and Baseline Characteristics

Demographics and baseline characteristics will be summarized based on the OL-FAS for Part A, and presented by treatment group in parent study and overall.

Demographic data will include the following:

- Age at parent study baseline (in years)
- Sex (female and male)
- Ethnicity (Hispanic or Latino, not Hispanic or Latino, and not collected per local regulations)
- Race (White, Black or African American, Asian, American Indian or Alaska Native, Native Hawaiian or Other Pacific Islander, Not Collected per Local Regulations and Other)
- Geographic region (North America, Europe [including Australia])

Parent study baseline characteristics will include the following:

- Weight (kg)
- Height (cm)
- BMI (kg/m²)
- BMI z-score (for subjects ≤ 20 years old at baseline)

Stratification categories used in the parent study will include the following:

- Comparator group in parent study (TEZ/IVA comparator group, IVA comparator group)
- ppFEV₁ at Day -14 of parent study (<70 , ≥ 70)
- SwCl at Day -14 of parent study (<30 mmol/L, ≥ 30 mmol/L)

Disease characteristics based on the parent study will include the following:

- ppFEV₁ category at baseline (<40 , ≥ 40 to <70 , ≥ 70 to ≤ 90 , and >90)
- ppFEV₁ at baseline (continuous)
- Sweat chloride at baseline (continuous)
- CFQ-R respiratory domain score at baseline (continuous)
- Prior use of dornase alfa (Yes, No)
- Prior use of azithromycin (Yes, No)
- Prior use of inhaled antibiotic (Yes, No)

- Prior use of any bronchodilator (Yes, No)
- Prior use of any inhaled bronchodilator (Yes, No)
- Prior use of any inhaled hypertonic saline (Yes, No)
- Infection with *Pseudomonas aeruginosa* within 2 years prior to screening visit of parent study (Positive, Negative)

For subjects who received TC in the parent study, prior medication use refers to medication taken during 56 days before the first dose date of study drug in the parent study treatment period or medication taken during the Run-in period. For subjects who did not receive TC in the parent study, prior medication use refers to medication taken during 56 days before the first dose date of study drug in the OLS, if applicable. No statistical tests will be carried out to evaluate any baseline imbalance between treatment groups.

9.2.3 Medical History

Medical history (referenced to the start of parent study) will be coded by using the Medical Dictionary for Regulatory Activities (MedDRA). For the OL-FAS for Part A, medical history will be summarized descriptively by treatment group in parent study and overall and by System Organ Class (SOC) and Preferred Term (PT). The corresponding data listing will also be provided.

9.2.4 Prior and Concomitant Medications

Medications will be coded using the World Health Organization-Drug Dictionary (WHODrug) and categorized as follows:

- **Prior medication:** any medication that was administered during the 56 days before the first dose date of study drug in the OLS.
- **Concomitant medication:** medication continued or newly received during the TE Period for Part A for the OLS.
- **Post-treatment medication:** medication continued or newly received after the TE Period for Part A for the OLS.

A given medication may be classified as a prior medication, a concomitant medication, a post-treatment medication, both prior and concomitant, both concomitant and post-treatment, or all three categories of prior, concomitant, and post-treatment.

If a medication has completely missing or partially missing start/stop date and if it cannot be determined whether it was taken before the first dose date of the OLS, concomitantly during the TE Period for Part A for the OLS, or after the TE Period for Part A for the OLS, it will be considered in all 3 categories of prior, concomitant, and post-treatment medication. Details for imputing missing or partial start and/or stop dates of medication are described in Section 12.2.

For the OL-FAS for Part A, prior medications and concomitant medications will be summarized descriptively by: 1) treatment group in parent study and overall, Preferred Name (PN); and 2) treatment group in parent study and overall, anatomic class (ATC) level 1, ATC level 2, and PN. Post-treatment medications will be listed for each subject, if applicable.

9.2.5 Study Drug Exposure

Duration of study drug exposure (in days) will be calculated as: last dose date of study drug in the OLS – first dose date of study drug in the OLS + 1, regardless of study drug interruption. For subjects who enroll in another qualified Vertex study before completing this study and resume participation in this study, time spent in the other study will be excluded.

Study drug exposure (in weeks) during OL safety period for Part A for the OL-SS for Part A will be summarized descriptively by the number of subjects (n), mean, SD, median, min, and max. It will also be summarized into the following categories: ≤ 24 weeks, >24 to ≤ 48 weeks, >48 to ≤ 72 weeks, >72 to ≤ 96 weeks, >96 weeks. Additionally, the total study drug exposure, defined as the sum total of the study drug exposure across all subjects (in patient-weeks and patient-years), will be provided. The summary will be presented by treatment group in parent study and overall.

9.2.6 Study Drug Compliance

Study drug compliance for the OL efficacy period for Part A will be calculated as: $100 \times [1 - (\text{total number of days of study drug interruption}) / (\text{duration of study drug exposure in days})]$. A study drug interruption on a given day is defined as an interruption of any study drug on that day. For subjects who enroll in another qualified Vertex study before completing this study and resume participation in this study, time spent in the other study will be excluded.

Percentage of study drug compliance will be summarized based on the OL-FAS for Part A and presented by treatment group in parent study and overall. Percentage of study drug compliance will be summarized descriptively by the number of subjects (n), mean, SD, median, min, and max. It will also be summarized in categories: $<80\%$ and $\geq 80\%$ using frequency tables.

In addition, percentage of tablets taken during the OL efficacy period for Part A will be calculated using the following formula: $100 \times [(\text{total number of tablets dispensed}) - (\text{total number of tablets returned})] / (\text{total number of tablets planned to be taken per day} \times \text{duration of study drug exposure in days})$. Summary similar to those for the study drug compliance will be produced based on the OL-FAS for Part A.

9.2.7 Important Protocol Deviations

An important protocol deviation (IPD) is a deviation that may significantly affect the completeness, accuracy, or reliability of the study data or that may significantly affect a subject's rights, safety, or well-being. A protocol deviation review team will categorize IPDs according to the Protocol Deviation Plan during the study.

IPDs during the OL Efficacy period for Part A will be summarized descriptively based on the OL-FAS for Part A and presented by treatment group in parent studies and overall. Additionally, IPDs during the OL Efficacy period for Part A will be provided in an individual subject data listing. IPDs will be analyzed only as part of final analysis.

9.3 Efficacy Analysis

The parent study baseline will be used to calculate the change from baseline for continuous efficacy endpoints unless otherwise specified. Data of continuous endpoints at visits in the parent study will be analyzed using the same mixed-effects model for repeated measures (MMRM) approach as described in the SAP for the parent study. The resulting estimates will be identical to

what is in the CSR of the parent study. Similarly, data of continuous endpoints at visits in the OL efficacy period for Part A will be analyzed using a separate MMRM. The results obtained from the parent study and OLE efficacy period will be displayed one followed by the other.

The focus of the efficacy analysis is to characterize the long-term treatment effects using change from baseline for each treatment group in the parent study. *P* values will not be presented.

9.3.1 Analysis of Primary Efficacy Endpoint

Not applicable since efficacy is not a primary objective.

9.3.2 Analysis of Secondary Efficacy and Pharmacodynamic Endpoint

9.3.2.1 Definition of Variables

Percent predicted forced expiratory volume in 1 second (ppFEV₁): Percent predicted FEV₁ is the ratio of FEV₁ (L) and predicted FEV₁ (L), expressed as a percentage. The predicted FEV₁ will be calculated using the Global Lung Function Initiative¹ (GLI). See Section 12.5 for more details.

Sweat chloride (SwCl): the SwCl value for a given visit will be calculated as the mean of the non-missing sweat chloride measurements obtained on the left and right arms at that visit. If one of the two arm measurements at a time point is missing, the other will be used as the mean. A volume ≥ 15 μL is required for an accurate determination of sweat chloride. Any results reported as having volume < 15 μL will be considered missing. Any sweat chloride values reported as > 160 mmol/L will be considered missing. Any sweat chloride values reported as < 10 mmol/L will be imputed as 10 mmol/L.

Body mass index (BMI): the BMI at each visit is calculated using the weight and height at each visit as follows:

$$\text{BMI} = \frac{\text{Weight (kg)}}{\text{Height}^2 (\text{m}^2)}$$

BMI z-score: the BMI score, adjusted for age and sex, will be referred to as BMI-for-age z-score (BMI z-score). The BMI z-score will be calculated by using Centers for Disease Control and Prevention (CDC) growth charts², with the age (in months) used for the calculation defined in Section 12.1.

Cystic Fibrosis Questionnaire-Revised (CFQ-R): The CFQ-R^{3,4,5} is a validated CF-specific instrument that measures quality-of-life domains. This study utilizes three different versions of CFQ-R:

- CFQ-R for Children ages 12 and 13
- CFQ-R for Adolescents and Adults (subjects 14 years and older)
- CFQ-R for Parents/Caregivers (subjects 13 years and younger)

In all three versions, specific question belonging to a domain is scored 1, 2, 3, or 4. The CFQ-R domain score, e.g., physical domain score or respiratory domain score, is defined as a scaled score as follows:

Scaled score for a domain = $100 \times (\text{mean (scores of all questions in the domain)} - 1)/3$, where the score from a negatively phrased question is first reversed, i.e., reversed score = $5 - \text{actual score}$, so that 1 always represents the worst condition and 4 the best condition. The

(scaled) domain score ranges from 0 (worst condition) to 100 (best condition). The scaled score for a specific domain will not be calculated if more than half of the questions in the domain have missing scores.

The (scaled) domain score from the CFQ-R for Children ages 12 and 13 and for Adolescent and Adults will be pooled within and across subjects for the analysis purpose.

9.3.2.1 Analysis Method

Absolute change from baseline in ppFEV₁

The MMRM for the parent study efficacy period will be same as that described in the SAP for Study 104. In the MMRM for the OL efficacy period for Part A, the absolute change from baseline in ppFEV₁ will be the dependent variable. The model will include treatment group (as randomized in parent study), visit, and treatment by visit interaction as fixed effects, with continuous baseline ppFEV₁ from parent study, continuous baseline SwCl from parent study and comparator group (IVA comparator versus TEZ/IVA comparator) as covariates.

The repeated-measures analysis will be based on the restricted maximum likelihood method assuming an unstructured covariance structure to model the within-subject errors. The denominator degrees of freedom will be based on the method proposed by Kenward-Roger⁶. If the model fails to converge due to the unstructured covariance assumption, a compound symmetry covariance structure will be used to model the within-subject errors. In the MMRM approach, assuming that the data are missing at random, no imputation of missing data will be performed.

The number of subjects, least-squares means (LS means) for absolute change from baseline at scheduled visits within each treatment group along with the corresponding standard error (SE), and 95% confidence interval (CI) will be presented. The LS means (\pm SE) for absolute change from baseline at each visit will also be plotted by treatment groups. For display purpose, the estimates and corresponding 95% CI obtained from both the parent study MMRM and OLS Part A will be summarized in a single summary table.

The main analysis will be conducted with the clinic spirometry data only. In addition, the descriptive statistics for raw values and absolute changes from baseline in ppFEV₁ by treatment group and visit will be presented for the OL efficacy period for Part A in OL-FAS for Part A.

Absolute change from baseline in SwCl

Analysis of this PD variable will be based on the same MMRM to the analysis of the absolute change from baseline in ppFEV₁. A descriptive summary of raw values and absolute changes from baseline will also be presented.

Absolute change from baseline in Weight, BMI and BMI Z-score (for subjects \leq 20 years of age at parent study baseline)

Analysis of these variables will be based on the same MMRM to the analysis of the absolute change from baseline in ppFEV₁. A descriptive summary of raw values and absolute changes from baseline will also be presented.

Absolute change from baseline in CFQ-R respiratory domain score

Analysis of this variable will be based on the same MMRM to the analysis of the absolute change from baseline in ppFEV₁. A descriptive summary of raw values and absolute changes from baseline will also be presented.

The analysis will include pooled CFQ-R RD score assessed at clinic and at home. An additional analysis may be performed to include only the clinic assessed CFQ-R RD score, if the home assessed data are assessed to be inconsistent with the clinic assessed data.

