12.3.3.2 Analysis of Secondary Efficacy Endpoints

The secondary endpoints include:

- **Absolute change in ppFEV₁**

One of the secondary efficacy endpoints is the absolute change in ppFEV₁ at visits in the open-label study, for subjects who receive at least 1 dose of study drug in the open-label study. The primary analysis for this secondary endpoint will be based on a mixed-effects model for repeated measures (MMRM), with the absolute change from baseline in ppFEV₁ as the dependent variable for visits in the open-label study. The model will be similar to the one used for the primary efficacy analysis in the parent study.

The details including sensitivity analyses and supportive analyses will be described in the SAP.

- **Absolute change in SwCl**

Analysis of this PD endpoint will be based on an MMRM similar to the analysis of the absolute change in ppFEV₁.

- **Absolute change in BMI**

Analysis of this endpoint will be based on an MMRM similar to the analysis of the absolute change in ppFEV₁.

- **Absolute change in BMI z-score**

Analysis of this endpoint will be based on an MMRM similar to the analysis of the absolute change in ppFEV₁.

- **Absolute change in body weight**

Analysis for this endpoint will be based on an MMRM similar to the analysis of the absolute change in ppFEV₁.

- **Absolute change in CFQ-R RD score**

Analysis of this endpoint will be based on an MMRM similar to the analysis of the absolute change in ppFEV₁.

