9.3.2.2 Subgroup Analysis

Subgroup analysis of absolute change from baseline in ppFEV₁ will be performed in a manner similar to that of the primary analysis of absolute change from baseline in ppFEV₁ for the following subgroup:

- Comparator group (TEZ/IVA comparator, IVA comparator)

A similar MMRM used for the primary analysis will be used for the subgroup analysis, where the covariate of comparator group (TEZ/IVA comparator, IVA comparator) from the MMRM will be removed. The adjusted means with 2-sided 95% confidence intervals will be provided. Note that the proposed subgroup analysis will be implemented only if there are at least 20 subjects in each treatment group. Due to potential small sample size, the results from above mentioned subgroup analysis, especially the comparison between two comparator groups, should be interpreted with caution.

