9.6.1 Analysis of absolute change from baseline in CFQ-R non-respiratory domain score

Analysis of these domains will be based on an MMRM similar to the analysis of the absolute change from baseline in ppFEV₁. The mean plot will not be produced for these domains.

10 Interim and DMC Analyses

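### Read literally, the MMRMs for CFQ-R RD, weight, BMI and BMI z-score leave out the endpoint's own baseline; the SAP should say which baseline each model uses (minor).

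*SAP*

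**What the plan says.** SAP 9.3.2.1 (Analysis Method) defines the open-label ppFEV1 model: parent-study treatment group, visit and their interaction as fixed effects, plus baseline ppFEV1, "continuous baseline SwCl from parent study and comparator group (IVA comparator versus TEZ/IVA comparator) as covariates".

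The other secondary endpoints refer back to that model. For weight, BMI and BMI z-score: "Analysis of these variables will be based on the same MMRM to the analysis of the absolute" change in ppFEV1. For CFQ-R RD: "Analysis of this variable will be based on the same MMRM to the analysis of the absolute" change in ppFEV1. Neither sentence names a different baseline covariate. SwCl is covered, because its baseline is already in the list.

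Elsewhere the wording is looser. Protocol 12.3.3.2 says "Analysis of this endpoint will be based on an MMRM similar to the analysis of the absolute" change in ppFEV1 and lists no covariates. SAP 9.6.1 says of the CFQ-R non-respiratory domains "Analysis of these domains will be based on an MMRM similar to the analysis of the absolute" change in ppFEV1. In SAP 9.3.2.2, where a covariate does change, the text says so: "where the covariate of comparator group (TEZ/IVA comparator, IVA comparator) from the MMRM will be removed".

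The output is LS means with SE and 95% CI within each parent-study group, without P values. SAP 9.3 puts the focus on long-term effects "using change from baseline for each treatment group in the parent study". Study 104 and open-label estimates go into a single summary table.

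**The concern.** For ppFEV1 and SwCl the model contains the baseline value of the endpoint itself. For the other four, read as written, it does not. A change score is usually correlated with its own baseline, so leaving that baseline out gives up some precision and leaves part of any chance baseline difference between the two parent-study groups in the side-by-side curves.

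The text also permits more than one model. A programmer could keep the three listed covariates, replace baseline ppFEV1 with the own baseline, or add the own baseline to all three, and claim compliance each time. SAP 9.3.2.1 plans no sensitivity or supportive analysis of the secondary endpoints that would show the difference.

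The intervals would also differ in meaning across the six endpoints. Those for ppFEV1 and SwCl are conditional on the observed mean of the endpoint's own baseline; the other four would not be.

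**Working it through.** **No figure to reproduce.** The plan gives no SD, correlation, precision target or group size. Its only number is about 250 expected subjects (Protocol 12.1, SAP 6.2). Everything else here is an assumption: two equal groups of n = 125, CFQ-R RD baseline SD s = 18, baseline-to-follow-up correlation ρ, and ratio k of follow-up SD to baseline SD.

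**Formulas** for the variance of one group's LS mean change at one visit, with LS means taken at the pooled baseline mean and the other covariates ignored:

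- Without own baseline: s²(1 + k² − 2ρk)/n
- With own baseline, as the model prints it: s²k²(1 − ρ²)/n
- With own baseline, over repeated samples (true): s²[k²(1 − ρ²) + (1 − ρk)²/2]/n

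The last term arises because the pooled baseline mean is itself random; the printed SE treats it as fixed.

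**CFQ-R RD, k = 1.** Example at ρ = 0.5, in units of s²/n: without 1.000, printed 0.750, true 0.750 + 0.25/2 = 0.875. True SE cut = 1 − √0.875 = 6.5%; printed cut = 1 − √0.750 = 13.4%.

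| ρ | SE without | True SE with | True cut | Printed cut | True 95% half-width saved |
|---|---|---|---|---|---|
| 0.5 | 1.610 | 1.506 | 6.5% | 13.4% | 0.20 of 3.16 points |
| 0.6 | 1.440 | 1.366 | 5.1% | 10.6% | 0.14 of 2.82 points |
| 0.7 | 1.247 | 1.199 | 3.8% | 7.8% | 0.09 of 2.44 points |

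The true gain is worth 14%, 11% and 8% more subjects (1/0.875, 0.800/0.720, 0.600/0.555).

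**Follow-up SD not equal to baseline SD.** CFQ-R RD at ρ = 0.7:

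- k = 1.2: true variance 0.7472 against 0.7600, a cut of 0.8%.
- k = 0.8: 0.4232 against 0.5200, a cut of 9.8%.

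Weight and BMI, true cut:

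| k | ρ = 0.90 | ρ = 0.95 | ρ = 0.98 |
|---|---|---|---|
| 0.9 | 4.9% | 5.4% | 7.9% |
| 1.0 | 1.3% | 0.6% | 0.3% |
| 1.1 | 0.0% | 0.4% | 2.9% |

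For BMI z-score the correlation is unknown and no figure is offered.

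**Coverage of the population mean change.** If the printed SE is too small by √(printed/true), a nominal 95% interval uses 1.96 times that ratio. At k = 1:

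- ρ = 0.5: 1.96 × √(0.750/0.875) = 1.81, about 93.0%.
- ρ = 0.7: 1.96 × √(0.510/0.555) = 1.88, about 94.0%.

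A single-visit simulation (8,000 runs, with ppFEV1, SwCl and comparator group in the model) gave 93.4%, 93.4% and 94.1% at ρ = 0.5, 0.6, 0.7, against 94.4 to 95.4% without own baseline. Coverage is lower where the SE gain is larger: at k = 0.8, ρ = 0.7, 1.96 × √(0.3264/0.4232) = 1.72, about 91.5%.

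**Other covariates.** When own baseline is itself correlated with baseline ppFEV1 and SwCl (0.35 and 0.10 assumed, 4,000 runs), the printed cut was 11.8%, 9.3% and 6.8%, and the empirical cut 6.3%, 5.6% and 3.3%. The picture does not change.

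**Baseline imbalance.** One SE of a chance difference is 18 × √(2/125) = 2.28 points. Without own baseline, (1 − ρ) of it stays between the curves: 1.14, 0.91 and 0.68 points at ρ = 0.5, 0.6, 0.7.

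**The case against.** **Substitution may be what the authors meant.** The outcome has to be swapped in any reading, and swapping its baseline too is natural. The protocol and SAP 9.6.1 both use the looser wording, and SAP 2.1 declares no departure from the protocol. The subgroup sentence is a single instance, in a model where comparator group has to go because it defines the subgroup. This stands: a reader might infer that the SAP definitely drops the own baseline, and the documents do not establish that. They show only that the choice is unstated.

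**The literal covariate set is defensible.** It matches the three Study 104 stratification variables listed in SAP 9.2.2, with ppFEV1 and SwCl as continuous values. That makes it a coherent choice, but the SAP does not give it as the reason.

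**The Study 104 models matter and cannot be seen.** The protocol synopsis says efficacy methods will be similar to the parent study, and both sets of estimates share a table. Changing only the open-label model could make the two halves less comparable. This stands and shapes the fix.

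**The gain is not free.** A reader might take the printed SE cut of up to 13% as the benefit. About half of it comes from treating the baseline mean as fixed, and coverage of the population mean change falls below 95%. The ppFEV1 and SwCl models have an issue of the same kind.

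**Little depends on it.** There are no P values and no planned group contrast. Descriptive changes are also tabulated, and SAP 9.2.2 lists "CFQ-R respiratory domain score at baseline (continuous") by parent group, so an imbalance would be visible. This stands and keeps the point minor.

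**Conclusion.** A minor specification gap. As written, four of the six secondary endpoint models carry no own baseline, and no passage says that it is substituted.

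Under the stated assumptions, including it reduces the true within-group SE for CFQ-R RD by about 4 to 7% at equal SDs. At ρ = 0.7 this runs from about 1% if the follow-up SD is 20% larger to about 10% if it is 20% smaller. For weight and BMI the true reduction is 0.3 to 1.3% at equal SDs, 0 to 3% if the follow-up SD is 10% larger, and about 5 to 8% if it is 10% smaller. All correlations, SDs and group sizes are assumed. If substitution was intended, nothing is lost and only the wording needs work.

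A reader might go further and call the planned estimates biased through dropout. In one illustration at SD 18, with about 26% missingness driven by own baseline, omitting it shifted the later-visit mean by about 0.4 points. Nothing in the documents indicates such a mechanism, so that is not claimed. No P value, planned contrast or primary safety conclusion is affected.

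**What to change.** In SAP 9.3.2.1 and 9.6.1:

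- State that each open-label MMRM includes the parent-study baseline of the endpoint analysed; for CFQ-R non-respiratory domains, the matching domain.
- Keep comparator group, and say whether baseline ppFEV1 and baseline SwCl are retained.
- Check the choice against the Study 104 models. If those lack the own baseline, footnote the difference in the combined table.
- Note that the within-group CI is then conditional on the observed baseline mean, as it already is for ppFEV1 and SwCl.

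The cost is one or two sentences, one covariate in the code, a look at the Study 104 SAP and possibly a footnote. No subject is lost and nothing new is collected, since the change score already needs the baseline value. The statistical price is the slight under-coverage shown above.
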